8. STUDY DRUG/DEVICE/BIOLOGIC ADMINISTRATION/ASSIGNMENT

8.1: Study Drug/Device/Biologic:

Influenza vaccines will be administered using age-appropriate guidelines in years 1 and 2 of the study. In year 2, all subjects will be administered IIV during a fall study visit in the VRU.

- Live vaccine will consist of Flumist Quadrivalent (MedImmune Vaccine), supplied in a pre-filled, single-dose intranasal sprayer. Each 0.2 mL dose contains $10^{6.5-7.5}$ fluorescent focus units of live attenuated influenza virus reassortants of each of the 4 strains (A/H1N1, A/H3N2, B/Yamagata and B/Victoria). Each dose is formulated in a sucrose phosphate buffer and may contain residual amounts of ovalbumin, gentamicin, and EDTA. Flumist contains no preservatives.
- Inactivated vaccine will consist of Fluzone Trivalent or Quadrivalent vaccine. This vaccine is approved for use in persons 6 month of age and older. It consists of a split and chemically inactivated influenza virus and is formulated to contain 7.5 mcg of each HA protein per 0.25 mL vaccine in sodium phosphate-buffered isotonic sodium chloride solution. This vaccine also may contain 12.5 mcg of thimerosal and trace amounts of formaldehyde in each 0.25 mL dose.

8.2: Dosage of Study Drug/Biologic

All influenza vaccines will be administered at the recommended doses for age:

- LAIV: Flumist Quadrivalent (MedImmune) 0.2 mL administered intranasally
- IIV: Fluzone 0.25 mL administered intramuscularly to children between 6 and 35 months of age
 - Children in cohort 2 (6-12 months of age) who are receiving influenza vaccine for the first time will receive 2 doses separated by 28 days +14 days

8.3: Study Enrollment/Randomization:

We plan to enroll a cohort of 60 children who have previously been vaccinated with at least 2 doses of IIV and who are between the ages of 24 and 35 months into vaccination cohort 1. These children will be block randomized to receive either LAIV (n=30) or IIV (n=30) in groups of 5 unless a history of isolated wheezing in the past year is present. As LAIV is not indicated in children with a history of recent wheezing, eligible children who give a history of isolated wheezing will be defaulted to receive IIV.

Infants between the ages of 6 months and 1 year of age receiving IIV before influenza reaches epidemic levels in the community will be eligible to enroll in the vaccination arm of cohort 2. These infants will not be randomized as they can only receive IIV. Two doses of IIV separated by 28 days will be administered to these children as they will be influenza-vaccine naïve. Infants between 3 and 12 months of age who are unvaccinated and present with influenza-like illness will be eligible to enroll in the infection arm of cohort 2.

8.4: Accountability of Investigational Supplies:

Some children will receive their first dose of influenza vaccine at the time of study enrollment in the office of their primary care physician. The clinic will be responsible for storing and maintaining these vaccines as recommended by the manufacturer. A supply of both vaccines will also be stored in a secure, limited-access, temperature monitored refrigerator at 2°C to 8°C in the VRU until needed. The temperature of the storage unit will be monitored throughout the duration of the study and documentation of proper storage will

be maintained. In the event of accidental deep-freezing or disruption of the cold chain, the vaccines will not be administered.

8.5: Subject Withdrawal of Study Drug

No medications will be chronically administered as part of this study.

8.6: Emergency Drug Disclosure:

Vaccine administration will not be blinded.

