2. STUDY DESIGN:

2.1: Overview:

This study will be conducted as a single center, prospective, open-label evaluation of different methods of priming on the anti-influenza CD4 T cell and antibody response in young children. It is anticipated that this study will last 3 years, with approximately 1 year of follow up for each subject. The study objectives are to evaluate the specificity and functional potential of the CD4 T cell response and the quantity, breadth and avidity of the neutralizing antibody response following either influenza infection or receipt of different types of licensed influenza vaccine as follows:

- Primary objective: To comprehensively evaluate the specificity and functional potential of CD4 T cell responses on a single cell level using intracellular cytokine staining following restimulation with pools of HA and NP peptides

Secondary objectives will include:

- To assess the full spectrum of antigen-specific CD4 T cell cytokine and chemokine production using multiplex cytokine assays
- To perform in depth characterization of the specificity of the CD4 T cell response following influenza vaccination or infection by Elispot assay
- To evaluate the humoral immune response that develops in response to infection or administration of the LAIV or IIV vaccines
- To determine the frequency of HA-specific memory B cells established using these priming conditions
- To determine the influence of the CD4 T cell response on the breadth and avidity of the post-vaccination antibody response using arrayed imaging reflectometry to rapidly quantify antibody levels against multiple HA proteins, microneutralization assays to quantify neutralizing antibody titers against different viral strains, and enzyme linked immunosorbent assays to determine HA antibody avidity and quantify stalk reactive antibody

[figure not shown]

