The age range of the first cohort of children was chosen because children first become eligible to receive LAIV at the age of 24 months. Thus, the age range of 24 through 35 months will capture children receiving LAIV for the first time. A block randomization scheme will be used as there is a large population of children with a past history of isolated wheezing as a result of viral illnesses such as bronchiolitis that have been shown to respond

equivalently to influenza vaccine (59, 74, 75). We feel that including this population of children in the study will improve recruitment and allow for broader applicability of our study results, but as these subjects are not eligible to receive LAIV (17, 18), their inclusion also precludes a completely blinded randomization scheme. With block randomization, eligible subjects will be enrolled to receive either LAIV or IIV in groups of 5 unless a history of isolated wheezing in the past year is present, in which case they will be defaulted to receive IIV as long as no other exclusion criteria are present.

The age range of the second cohort was chosen to enroll infants in their first influenza season with no history of prior exposure to influenza virus. Thus, this cohort will allow examination of the true primary response to influenza infection or inactivated vaccination. Children between 6 and 12 months of age who have not previously had an influenza infection or vaccination will be eligible to participate in the vaccination group. All of these children will receive IIV, as LAIV is not approved for children this age. This cohort will receive a prime-boost vaccination series, with vaccine doses separated by 28 (+ 14) days as recommended by the AAP and ACIP (17, 18). To minimize blood draws, we will only interrogate the immune response following the second vaccine dose. Children between 3 and 12 months of age who present with an influenza-like illness and have no previous history of influenza vaccination will be eligible to participate in the infection group. Study personnel will obtain nasal swabs from potential subjects for a rapid influenza antigen test on illness presentation (typically this occurs at day 3-4 post illness onset). If positive, they will be eligible for further study participation. Influenza real-time RT-PCR will be used to confirm rapid antigen test results, however these results will not be available in time to influence subject enrollment.

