3. CHARACTERISTICS OF THE RESEARCH POPULATION

3.1: Subject Characteristics

a. Number of Subjects: It is anticipated that this study will enroll a total of approximately 180 subjects. This includes 60 children between the ages of 24 and 35 months in the first cohort. These children will be divided equally into two groups of 30, with one group receiving IIV and the other receiving LAIV as described above. We expect to screen up to 120 subjects into the second cohort, of whom 45 will be enrolled in the full study and evaluable. This will include 30 children between the ages of 6 months and 1 year that will receive IIV and 15 children between the ages of 3 months and 1 year who become naturally infected with influenza virus. However, in order to enroll these 15 naturally infected children, we anticipate having to screen up to 90 children with signs of influenza like illness during the height of seasonal influenza circulation, as only a small number of these children will have respiratory infections as a result of influenza virus infection.

b. Gender and Age of Subjects: It is anticipated that there will be an approximately equal distribution of males and females enrolled. This will include 60 children between the ages of 24 and 35 months in the first cohort and up to 120 children between the ages of 3 months and 1 year in the second cohort, of whom 45 will be evaluable.

c. Racial and Ethnic Origin: It is anticipated that the demographic distribution of enrollment will approximately resemble that of the City of Rochester, which is about 40% Caucasian, 40% African-American, 15% Hispanic, and 5% other. No subject will be excluded because of their racial or ethnic origin.

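### Cohort 1 is block randomised in undefined groups of 5: as a block size this is never 1:1, and as runs of one vaccine it makes at least 80% of assignments foreseeable

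*Combined protocol and SAP*

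**What the plan says.** Section 8.3 opens with "We plan to enroll a cohort of 60 children" and says they will be "block randomized to receive either LAIV (n=30) or IIV (n=30) in groups of 5". Section 2.1 uses the same wording. Section 3.1(a) gives the intended ratio: "These children will be divided equally into two groups of 30".

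Section 2.2 describes the scheme differently: "eligible subjects will be enrolled to receive either LAIV or IIV in groups of 5".

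Not every child is randomised. Under section 8.3, "eligible children who give a history of isolated wheezing will be defaulted to receive IIV". Section 2.2 says of these children that "their inclusion also precludes a completely blinded randomization scheme".

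Section 2.1 calls the study a "single center, prospective, open-label evaluation", and section 8.6 states: "Vaccine administration will not be blinded".

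The text does not say whether 5 is the block size, the number per arm within a block, or a run of children given one vaccine. It does not say how the sequence is generated, who holds it, or when an assignment is revealed.

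**The concern.** Five is an odd number in a two-arm 1:1 design, so it cannot be the size of a block that is balanced within itself. The wording of section 2.2 can be followed faithfully by giving five children in a row the same vaccine. Staff at one site who give unblinded vaccine see every past assignment, so under that scheme they would know most of the coming ones.

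LAIV against IIV in cohort 1 is the only randomised comparison, since section 8.3 does not randomise cohort 2. Someone who knows the next vaccine can bring a family's enrolment forward, delay it, or ask about wheezing more or less searchingly. The wheezing question matters most here because the answer itself moves a child to IIV. A difference in CD4 T cell response could then partly reflect who was enrolled when.

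**Working it through.** **Inputs.** 60 children, 30 per arm, groups of 5 (section 8.3), so 60/5 = 12 groups. Difference 0.3 and SD 0.4 on the log10 scale, stated power 0.815 (section 13.1). The significance level behind the power table is not stated; two-sided 0.05 is assumed.

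**The plan's own figure.** For the two-sample t-test with 30/30, the noncentrality is 0.3 / (0.4 × √(1/30 + 1/30)) = 2.905 on 58 degrees of freedom, giving power 0.815. This reproduces the plan. The plan gives no figure for balance or predictability, so those are computed below.

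**Measures.** *Certain* is the share of assignments fully determined by earlier ones. *Guessed* is the expected share called correctly by someone who knows the scheme, sees all past assignments and always picks the likelier vaccine.

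**Reading A: 5 is the block size, with both vaccines in each block.** Each block is 3:2 or 2:3.

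- Same 3:2 mix throughout: 12 × 3 = 36 against 12 × 2 = 24. Guessed, averaged over the five positions: (0.6 + 0.6 + 0.7 + 0.7 + 1.0)/5 = 0.72. Certain: 30%.
- Direction of each block random: the LAIV total is 24 + Binomial(12, 0.5), ranging from 24 to 36. P(exactly 30/30) = 924/4096 = 0.226, and P(27 to 33) = 0.961. With all 20 sequences equally likely, guessed is (0.5 + 0.6 + 0.6 + 0.7 + 0.7)/5 = 0.62. Certain: 10 of 100 sequence positions, 10%.
- Six blocks each way would give exactly 30/30, but the plan does not specify this.

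**Reading B: five consecutive children receive one vaccine.** Once the first child of each group is treated, the other four are known: 12 × 4 = 48, and 48/60 = 80%.

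- Each group's vaccine decided independently: guessed (48 + 12 × 0.5)/60 = 90%.
- Six groups per arm in random order: the arms are exactly 30/30. A further 6/7 + 6/7 = 1.71 group openers are certain on average, so (48 + 1.71)/60 = 82.9% are certain. Expected correct guesses of openers are 7.72, so (48 + 7.72)/60 = 92.9% are guessed.
- Only 12 units are randomised, whereas the tests in section 13.2 treat the 60 children as individually assigned.

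**Reading C: five per arm in blocks of 10.** Balanced within each block.

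| Scheme | 1:1 within block | Certain | Guessed |
|---|---|---|---|
| A, fixed 3:2 | no | 30% | 72% |
| A, random direction | no | 10% | 62% |
| B, independent groups | not applicable | 80% | 90% |
| B, six groups per arm | not applicable | 83% | 93% |
| C, blocks of 10 | yes | 17% | 65% |
| For comparison: fixed blocks of 4 | yes | 33% | 71% |
| For comparison: fixed blocks of 6 | yes | 25% | 68% |

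**Effect of the wheezing default.** With children eligible for either vaccine randomised 1:1 and the rest sent to IIV, a wheezing share w gives 30(1 − w) on LAIV out of 60. The documents give no w. Assumed values of 10%, 20% and 30% give 27:33, 24:36 and 21:39.

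**The case against.** Sections 2.1 and 8.3 say block randomised, and the sentence in section 2.2 opens by invoking block randomisation. A statistician building the list might well take 5 as a block size, or as five per arm, and never produce runs. This is fair, and it makes the runs-of-five figures conditional. The text still leaves the choice to whoever writes the list, and section 2.2 permits the worst one.

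A reader might infer that groups of five cannot balance the arms. That is wrong: twelve groups can reach 30/30 under every reading except a fixed 3:2 mix. Nor is any single reading both unbalanced and mostly predictable; mixed blocks fail 1:1 within a block but leave only 10% to 30% certain, while runs of five are predictable but can balance exactly.

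Two further arguments do not carry the point. Imbalance costs little power: at 36/24 the noncentrality is 0.3 / (0.4 × √(1/36 + 1/24)) = 2.846 and power is 0.799. And even blocks are not in themselves harder to guess: 4s and 6s score 71% and 68%, against 62% for blocks of five with random direction.

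The primary endpoint is a laboratory assay, and primary-care providers identify candidates (section 4.1). Both limit the room for bias, but neither conceals the next assignment. Section 2.2 admits that the scheme is not completely blinded. Blinding and concealment differ, however: including wheezing children does not prevent hiding the sequence for those eligible for either vaccine.

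**Conclusion.** The point stands as an undefined allocation rule with one seriously predictable reading. The size depends on that reading: under runs of five, 80% to 83% of assignments are certain and 90% to 93% guessable; under mixed blocks of five, no block is 1:1 and, with random direction, exact 30/30 has probability 0.23. The predictability figures assume staff know the scheme and see all past assignments, which open-label vaccine at one centre makes plausible. Absence of concealment means that none is described in the supplied text.

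The consequence is weakened protection against selection bias. A reader might go further and conclude that enrolment was manipulated or that the comparison is void; nothing in the documents supports that. The change should be made because the comparison is the study's only randomised one and the remedy is nearly free.

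**What to change.** Replace the groups-of-5 wording in sections 2.1, 2.2 and 8.3 with one description:

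1. Record consent, eligibility and wheezing history before any assignment is seen.
2. For children eligible for either vaccine, assign 1:1 from a computer-generated list of permuted blocks of randomly varying even size, for example 4 and 6. Do not disclose the sizes to enrolling staff.
3. Conceal each assignment until step 1 is complete, by sealed envelopes or a database module. Section 5.11 mentions an online study database but describes no randomisation function, so envelopes may be simpler. Whichever is used must also work in the primary-care offices where some first doses are given (section 8.4).
4. State whether 30/30 refers to the randomised children or to all of cohort 1. The new list alone does not secure 30/30 overall, because of the wheezing default.

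The benefit comes mainly from ruling out runs of five and from concealment, with 1:1 balance within completed blocks as a further gain. The cost is a new list and a few sentences of protocol text; no additional children are needed.

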Figure 2: Expansion of CD4 T cells directed against conserved peptides is seen following pandemic H1N1 vaccination, with a correlation between the development of an HA-specific CD4 T cell response and neutralizing antibody titer. Subjects received the monovalent inactivated subvirion A/California/07/09 vaccine and CD4 T cell responses against conserved and nonconserved peptide pools were examined by IFN γ Elispot assay using CD8 and CD56 depleted PBMCs. While a response to HA (A) and NP/M1 (B) peptide pools expected to be conserved compared to recently circulating H1N1 strains was detected, little response to peptides expected to be unique to this virus was seen in subjects without prior immunity (C). Error bars represent the standard error of the mean and P-values calculated using Wilcoxon signed rank test. Development of a CD4 T cell response was correlated with the maximum microneutralization titer achieved (D). R- and p-values determined using the Spearman correlation coefficient.

- To evaluate in an unbiased way the influence of previous influenza exposure on PBMC gene expression patterns using RNA-seq analysis
- To assess the mucosal immunity established by these modes of priming and determine whether any initially established differences in mucosal immunity are maintained on subsequent rechallenge with IIV

To accomplish these objectives, we plan to enroll a cohort of 60 children who have previously been vaccinated with at least 2 doses of IIV and who are between the ages of 24 and 35 months into cohort 1. These children will be block randomized to receive either LAIV (n=30) or IIV (n=30) in groups of 5 unless a history of isolated wheezing in the past year is present. As LAIV is not indicated in children with a history of recent wheezing, otherwise eligible children who have a history of wheezing will be defaulted to receive IIV. Children will have a blood draw and nasal wash on study entry and again at days 10 (+ 4 days/- 2 days) and 24 (+/- 4 days) post vaccination. They will then be followed through to the subsequent influenza season, when they will be rechallenged with IIV with blood draws and nasal washes pre-vaccination and again at days 10 (+ 4 days/- 2 days) and 24 (+/- 4 days) post vaccination (Figure 3).

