- Between 6 and 12 months to participate in the vaccination arm of cohort 2 (cohort 2A)
- Between 3 and 12 months to participate in the natural infection arm of cohort 2 (cohort 2B)
- Gestational age of ≥ 37 weeks at birth
- Parent/guardian can provide informed consent
- Available for the duration of the study
- History of previous IIV administration **ONLY** for participation in cohort 1
- Acute illness documented to be due to influenza virus **ONLY** for participation in the natural infection arm of cohort 2 (cohort 2B)

b. Exclusion Criteria:

- Immunosuppression as a result of an underlying illness or condition (including HIV or a primary immunodeficiency syndrome)
- Active neoplastic disease
- Use of potentially immunosuppressive medications currently or within the past year (including chemotherapeutic agents) or chronic (>2 weeks) use of oral or inhaled steroid therapy
- A diagnosis of asthma requiring chronic controller medication
- Previous administration of influenza vaccine in the current influenza season
- Receipt of immunoglobulin or another blood product within the year prior to study enrollment
- An acute illness within the previous 3 days or temperature $>38^{\circ}$ on screening **EXCEPT** for participation in the natural infection arm of cohort 2 (cohort 2B)
- A contraindication to influenza vaccination **EXCEPT** infants between 3 and 5 months presenting with natural influenza infection whose only contraindication is their current age

3.3: Discussion of Subject Population:

The main objective of this Study is to evaluate the specificity and functional potential of the CD4 T cell response and the quantity, breadth and avidity of the neutralizing antibody response following influenza infection or vaccination. In order to eliminate potential confounding factors, we plan to exclude any subject who has an acute or chronic medical condition that may result in immunosuppression. Also excluded will be potential subjects that have recently received immunosuppressive medications or blood products that could potentially interfere with vaccine immunogenicity. This exclusion will include children with a history of asthma who require chronic controller medicines, including inhaled steroids. Children with only a history isolated wheezing not on chronic controller therapy will be allowed to participate, although they will not be administered LAIV.

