The only at-home study activity required by the parents is to record any adverse events or symptoms of illness in the memory aids and contact study personnel if symptoms consistent with an influenza-like illness develop. It is possible that parents will not comply with this request. However, we will also obtain a sample of blood for measurement of baseline CD4 T cell and antibody responses at each subject's presentation for seasonal IIV administration in study year 2. If CD4 T cell and antibody responses increase between the final visit in study year 1 and day 0 in study year 2, it will provide strong evidence of that subject having had an undocumented influenza infection during the previous influenza season. These subjects will be noted and data will be analyzed both including and excluding these subjects to determine the effect they have on the results obtained.

5.6: Data and Specimen Banking for Future Research Use:

Subjects will be asked for permission to keep any remaining specimens for possible use in future research studies. All biological specimens will be assigned a unique identifying number which will identify subject and visit information, allowing confidentiality to be maintained. The specimens will be stored in secure facilities within the University of Rochester. Use of specimens remaining for additional studies not described in the original protocol must be approved by the IRB and will only be considered for those subjects who have consented to future research use of their specimens. There are no benefits to subjects in the collection, storage and subsequent research use of specimens. Information from additional testing will not be provided to the subject or in any way entered into their medical record.

5.7: Genetic/Genomic Research Activities:

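### The plan has no LAIV v IIV analysis limited to randomised children, although children with recent wheeze are placed in the IIV arm by rule

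*Combined protocol and SAP*

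**What the plan says.** **Assignment.** Sections 2.1 and 8.3 block-randomise 60 children of 24 to 35 months to LAIV or IIV in groups of 5, except those with isolated wheeze in the past year. Section 8.3 words the exception as follows, LAIV being ruled out for "children with a history of recent wheezing, eligible children who give a history of isolated wheezing will be defaulted to receive IIV". Section 2.1 has the same rule: "otherwise eligible children who have a history of wheezing will be defaulted to receive IIV". Section 2.2 repeats the rule: "in which case they will be defaulted to receive IIV as long as no other exclusion criteria are present". Section 3.3 confirms that these children enter the study but never the LAIV arm: "Children with only a history isolated wheezing not on chronic controller therapy will be allowed to participate, although they will not be administered LAIV".

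**Reason given.** Section 2.2 describes such children as a large population. It says including them helps recruitment and applicability, and cites references 59, 74 and 75 for an equivalent response to influenza vaccine.

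**Numbers.** Section 3.1: "These children will be divided equally into two groups of 30". Section 13.1 gives power 0.815 for 30 v 30.

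**Analysis.** For Aim 1, Section 13.2 plans two-sample t-tests (or Wilcoxon) at each time point and a mixed model whose only group term is LAIV or not. For Aim 3 it compares the same groups, with the two infant groups, by ANOVA (or Kruskal-Wallis), Tukey post-hoc tests and a similar mixed model. It has no term for wheeze or assignment route and no analysis restricted to randomised children. Section 10.1 says personal information is collected partly to deal with confounding, but names no method.

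**A precedent within the protocol.** For suspected undocumented influenza infection, Section 5.5 says "data will be analyzed both including and excluding these subjects".

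**The concern.** Recent wheeze can occur only in the IIV arm, by rule and not by chance. If wheeze, or whatever caused it, shifts CD4 T cell or antibody responses, part of the reported LAIV v IIV difference is a wheeze effect. Depending on its direction, that could create a difference or hide one.

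The point matters because this is the study's only randomised contrast. Of the vaccinated infants in cohort 2, Section 8.3 says: "These infants will not be randomized as they can only receive IIV". The infection arm is defined by presentation with illness. The protection that randomisation gives is available in cohort 1 alone, and Section 13.2 has no analysis that uses it intact.

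**Working it through.** **Inputs from Section 13.1:** SD 0.4 and difference 0.3 (log10), 30 per arm, Student's t-test. A two-sided 0.05 level is not stated beside the power table, but it reproduces the table.

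**Assumed, because the documents give no value:** w, the number of defaulted children (6, 12 or 18), and s, the log10 shift in their response (0, 0.1 or 0.2).

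**Step 1: the plan's figure.** SE = 0.4 × √(1/30 + 1/30) = 0.1033. Noncentrality = 0.3/0.1033 = 2.905 on 58 df, which gives power 0.815. This agrees with the protocol. The figure is correct for 30 v 30 pooled.

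**Step 2: bias of the pooled comparison, arms 30/30.** Bias = s × w/30. The false-positive rate is the chance that one unadjusted test rejects when the true vaccine difference is 0 and the apparent difference equals the bias.

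| w | s | Bias | False-positive rate |
|---|---|---|---|
| any | 0 | 0 | 0.050 |
| 6 | 0.1 | 0.1 × 6/30 = 0.02 | 0.054 |
| 12 | 0.1 | 0.1 × 12/30 = 0.04 | 0.067 |
| 6 | 0.2 | 0.2 × 6/30 = 0.04 | 0.067 |
| 12 | 0.2 | 0.2 × 12/30 = 0.08 | 0.119 |

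These rates ignore the slightly wider spread of a mixed IIV arm. A simulation that allows for it, with w = 12, gives 0.066 and 0.113 for shifts of 0.1 and 0.2.

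**Step 3: would the planned baseline test reveal the problem?** With w = 12 it would detect a baseline shift of 0.1 or 0.2 with probability 0.067 or 0.119 (the same calculation as Step 2). It cannot see a difference in response to vaccine.

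**Step 4: precision of a randomised-only comparison.** Suppose the total stays at 60 and the remaining 60 − w children are randomised 1:1 (an assumption; the documents give no ratio within the groups of 5). Each randomised arm then has (60 − w)/2 children.

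| w | Randomised arms | SE = 0.4 × √(2/n) | 0.3/SE | Power | 95% CI half-width |
|---|---|---|---|---|---|
| 0 | 30/30 | 0.1033 | 2.905 | 0.815 | 0.207 |
| 6 | 27/27 | 0.1089 | 2.756 | 0.772 | 0.218 |
| 12 | 24/24 | 0.1155 | 2.598 | 0.720 | 0.232 |
| 18 | 21/21 | 0.1234 | 2.430 | 0.660 | 0.249 |

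**Step 5: baseline adjustment.** Replace the SD by 0.4 × √(1 − r²) and give up one df. For an assumed baseline correlation r of 0.3 to 0.5, power is 0.849 to 0.909 for 30 v 30 pooled. For randomised-only it is 0.809 to 0.877 (27/27), 0.760 to 0.835 (24/24) and 0.700 to 0.781 (21/21). Adjustment helps both comparisons, so the adjusted figures should be compared with each other.

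**Step 6: could a wheeze covariate replace the restriction?** No. With no recently wheezing child on LAIV, a wheeze term in an otherwise unadjusted model returns LAIV minus non-wheezing IIV, which is the estimate from leaving those children out.

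**The case against.** The strongest defence is that this is a disclosed and reasoned choice. Section 2.2 gives its grounds, and Section 3.2 excludes asthma on controller medication and chronic steroid use, so only milder wheeze remains. The cited sources cannot be read here, so nothing in the documents shows that equivalence fails. That stands, and it limits the point to a missing check. The titles in the reference list do leave room for one: they concern high-risk children, an experimental model of allergic asthma, and children and adults with asthma. None names isolated wheeze at 24 to 35 months.

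Second, the size rests wholly on assumed inputs. This also stands. With 6 defaulted and a 0.1 shift the effect is negligible, and 12 defaulted would be 40% of the IIV arm.

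Third, a reader might infer that the randomised-only result must be the main estimate. The figures do not support that. Root mean squared error is √(SE² + bias²). With pooled arms of 30/30 against 30 v 24 or 30 v 18 randomised, a 0.1 shift gives 0.105 v 0.110 and 0.111 v 0.119, so pooling is more accurate. At a 0.2 shift the values are 0.111 v 0.110 (almost equal) and 0.131 v 0.119, so restriction does better with 12 defaulted. The choice is a trade-off between bias and precision.

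Fourth, Section 10.1 mentions confounding, and wheeze status must be known to assign the vaccine. That makes the check easy but does not plan it.

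Finally, Aim 3 includes non-randomised infants, so the argument applies there only to the LAIV v IIV pair.

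**Conclusion.** The concern holds as a gap in the analysis plan. Recent wheeze is confined to IIV by rule, Section 13.2 groups children by vaccine received, and no planned analysis shows whether the defaulted children move the result.

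Two stronger readings go beyond the documents. One is that the LAIV v IIV comparison is biased: the bias is zero if Section 2.2 is right, and otherwise depends on two quantities that the documents do not give. The other is that 0.815 is wrong: it reproduces exactly, but it describes 30 v 30 pooled and describes the randomised comparison only if 30 IIV children are randomised apart from those defaulted. That would take the total above 60. The protocol does not say how defaulted children count towards the 30.

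Over the illustrated range (6 or 12 defaulted, shift 0 to 0.2), the bias runs from 0 to 0.08 log10 against a planned difference of 0.3. The single-test false-positive rate runs from 0.050 to 0.119, before the planned Benjamini-Hochberg adjustment. The change is worth making because it is cheap and protects the one randomised contrast.

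**What to change.** - **Data:** record for each cohort 1 child whether the vaccine was randomised or defaulted.
- **Section 13.2:** for Aim 1, and for the same pair in Aim 3, pre-specify a LAIV v IIV comparison restricted to randomised children. Report it beside the all-children comparison, as Section 5.5 already does for undocumented infection. Adjust both post-vaccination comparisons for the baseline response already measured.
- **Main estimate:** the sponsor chooses which of the two leads and fixes that before results are seen. Vaccination is unblinded (Section 8.6), so a later choice could be driven by the data.
- **Sections 8.3 and 13.1:** state whether defaulted children count within the 30 IIV places. Say that 0.815 applies to 30 v 30 pooled, and give power for the expected randomised number.

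**Cost:** one data field, some wording and a little more analysis, with no new children or samples and no change to which vaccine any child receives. The randomised-only result is less precise (Step 4) and applies only to children without recent wheeze; the all-children result keeps the broader applicability that Section 2.2 seeks.

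**Limit:** the pair of results will not prove equivalence. With 12 defaulted and 24 randomised IIV children, the wheeze shift itself has SE 0.4 × √(1/12 + 1/24) = 0.141, too wide to exclude 0.1 or 0.2. What the randomised-only comparison adds is an estimate that does not depend on equivalence.
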